## Construct Validity

Construct validity essentially assesses the sharpness of a tool, in this context addressing the question: can the simulator be used to discriminate between a novice and an expert. Mean assessment scores generated by Orbis-FundamentalVR MSICS simulator will be compared between two cohorts of surgeon: novice and expert. There will be 5 in each cohort, each performing 3 cases. The first case will be disregarded and the mean of the remaining two cases will be recorded and analyzed.

Participants in the construct validity of assessment scores will be recruited from three centers.

## Face Validity

Face Validity will be assessed by survey and response to the questions:

- “Do you think the Orbis-FVR MSICS simulator is an appropriate way for trainees to learn manual small incision cataract surgery?”
- “Do you think the Orbis-FVR MSICS simulator is an appropriate way to assess trainees’ MSICS surgical skill?”

Responses will be evaluated on a 5-point Likert scale anchored at ‘1=strongly disagree’ and ‘5=strongly agree’.

A total of ten experts will be selected as participants in the face validity of the VR simulator. Recruited from all locations participating in the primary randomized control trial (Bangladesh, China, Ethiopia, India, Bangladesh, Togo, UK and USA).

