Outcome measures	
Assessments and follow-up time points are at baseline and 1 month.
 
Primary outcome measure: mean specific simulated surgical competency assessment score at one-month post-training intervention between groups (assessed using Sim-OSSCAR) (Appendix 4).
 
Secondary outcome measures:
 

• Assessment scores generated by Orbis-FVR Simulator pre- and post-intervention.

• Step-specific analysis: mean differences in Sim-OSSCAR score for the seven interactive steps assessed (incision, tunnel, AC entry, CCC, mobilization, removal and IOL). Total possible score 14.

• Self-reported confidence ratings (10-point Likert scale) in MSICS skills, and ophthalmic surgical skills

 
Further Exploratory Analysis:
 

• Construct validity study comparing scores generated by Orbis-FVR simulator between two cohorts of novice and expert MSICS surgeons.

• Face validity study subjectively assessing a group of expert MSICS surgeons' views of the Orbis-FVR simulator as representing MSICS

• Qualitative study of the acceptability and utility of the Orbis-FVR simulator as a training or assessment tool.

Population	The VR simulation surgical training, construct and face validity studies will be conducted in ophthalmology institutions in the Americas, Europe, Africa, and Asia. Participants will have follow-up assessments in their home training or work institutions in Bangladesh, China, Ethiopia, India, Mongolia, Togo, UK and USA.

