## Expected Outcomes of the Study

The outcome of this study is to test the Null Hypothesis that there is no association or relationship between the educational intervention of ‘intense virtual reality simulation-based surgical education’ for manual small incision cataract surgery.

If the analyzed data from this study does indeed statistically prove the alternate hypothesis, this study has the potential of proving, and providing the robust data, that simulation-based VR surgical education in MSICS improves competence and has face and construct validity.

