## Appendix 5. Acceptability and Utility Survey & Questionnaire

What is your gender?

- Male
- Female
- Other

Level of experience:

- Novice
- Expert

Likert scale statements

1. I was comfortable using the VR simulator
2. I found the VR simulator user friendly
3. I was able to easily use the VR simulator
4. The VR simulator tutorials were helpful
5. I was able to navigate the VR program with ease
6. The VR simulator helped me gain a better understanding of the MSICS procedure
7. The VR simulator improved my knowledge of the MSICS procedure
8. The VR simulator improved my MSICS skills
9. I found the VR simulator hardware user friendly
10. I would recommend training on the VR simulator to others

Responses will be evaluated on a 5-point Likert scale anchored at '1=strongly disagree' and '5=strongly agree'.

User feedback – open ended questions

- What elements of the simulator were most useful? Which steps or resources?
- Which were least useful?
- What change or improvement to the simulator program would you recommend?
- Do you think the VR simulator has a place in cataract surgical training?
- Any other comments?

Pre- and Post-Intervention Confidence Ratings:

- 1> On a scale of 1-10, how confident are you in your ophthalmic surgical skills?
- 2> On a scale of 1-10, how confident are you in MSICS skills?
- 3> What has impacted this confidence? [open question]

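### The two face-validity questions ask whether the simulator is appropriate for training and assessment, not whether it represents MSICS, so the exploratory face-validity objective has no planned measure

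*Combined protocol and SAP*

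**What the plan says.** The Study Summary, under Further Exploratory Analysis, gives the objective: "Face validity study subjectively assessing a group of expert MSICS surgeons' views of the Orbis-FVR simulator as representing MSICS". The next bullet is a separate qualitative objective: whether the simulator is acceptable and useful for training or for assessment. The Outcomes section also keeps the two apart, with face validity as item 4 and acceptability within item 5.

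The Face Validity section gives the measurement: "Face Validity will be assessed by survey and response to the questions". Two questions follow. The first concerns learning: "Do you think the Orbis-FVR MSICS simulator is an appropriate way for trainees to learn manual small incision cataract surgery". The second, in parallel terms, concerns whether the simulator suits the testing of trainees' skill.

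On scoring it says "Responses will be evaluated on a 5-point Likert scale anchored at" strong disagreement (1) and strong agreement (5). Ten experts are to answer.

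The Outcomes and Qualitative analysis sections mention an expert survey on a 5-point scale but give no further face-validity items. The only questionnaire supplied is Appendix 5, which covers acceptability and utility; a typical statement is "I found the VR simulator user friendly". Expected Outcomes of the Study says the trial could show that VR education in MSICS "improves competence and has face and construct validity".

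**The concern.** The objective and the questions are about different things. How well a simulator represents an operation is one matter; whether it is an appropriate way to teach or test trainees is another. An expert may think the simulated operation a poor likeness of MSICS and still regard any structured VR practice as a suitable teaching aid. That expert would answer 5 to the first question, and under the plan the answer would count towards face validity.

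What is at stake is one of the validity claims the study hopes to make. Validity appears in the project title and the aims, and face validity is named in the expected conclusion. Representation is also a fair question for this device: in Table 2, 10 of the 19 steps are animated and only 9 are interactive, and the Executive Summary presents immersive haptic VR as the untested element. The experts are the people best placed to judge this, and no planned question asks them.

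**Working it through.** No statistical calculation applies, and the plan gives no figure to reproduce: the ten experts are justified by precedent, not by a formula. The check compares the objective with the items.

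**Step 1. Match each question to an objective in the Study Summary.**

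| Face Validity question | Face-validity objective (represents MSICS) | Acceptability/utility objective (tool for training or assessment) |
|---|---|---|
| Appropriate for learning MSICS | not asked | matches the training part |
| Appropriate for assessing MSICS skill | not asked | matches the assessment part |

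The two questions correspond one to one with the two halves of the other objective.

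**Step 2. Look for a representation item in Appendix 5.**

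| Source | Items | Subject | Ask about representation |
|---|---|---|---|
| Face Validity section | 2 | appropriateness | 0 |
| Appendix 5, Likert statements | 10 | comfort and usability (5), tutorials (1), perceived learning (3), recommendation (1) | 0 |
| Appendix 5, open feedback | 5 | most useful, least useful, improvements, place in training, other comments | 0 |
| Appendix 5, confidence | 3 | two ratings and one open follow-up | 0 |

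Total: 2 + 10 + 5 + 3 = 20 items, of which 0 ask how well the simulator represents MSICS. The nearest statements concern a better understanding of the procedure, which is perceived learning. The open question on whether the simulator has a place in training is close to the first face-validity question.

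**Step 3. Size of the remedy.** The simulator has 9 interactive steps (Table 2).

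- Minimum: 1 overall item.
- Overall plus one single-attribute item per step: 1 + 9 = 10 items.
- Overall plus appearance and haptic feel asked separately per step: 1 + 2 × 9 = 19 items.

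Appearance and feel should not share one item, because a step that looks right but feels wrong could not then be scored.

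**The case against.** The strongest reply is that the documents never define face validity as realism. The Study Summary speaks of representing MSICS and mentions neither appearance nor haptic fidelity, and the only operational definition is the pair of questions in the Face Validity section. The expected conclusion is about VR education, and expert agreement that the tool suits learning and assessment is relevant to it. The second question also bears indirectly on representation, since it is hard to call a simulator a fair test of surgical skill if its tasks are unlike the operation. Appendix 5 is presented as an acceptability instrument, so its silence is less telling. Its open questions give experts room to report an unrepresentative step.

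Much of this stands, and it limits the point. A reader might infer that face validity here must mean sensory realism; the documents do not say so, and the point does not need it. A reader might also infer that the experts can supply no information at all on representation. That goes too far, because open comments and the second question may touch on it.

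The mismatch itself remains. The Study Summary names representation and separates it from acceptability and utility, and both questions fall on the other side of that separation. Indirect inference and chance remarks are not a planned measure.

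**Conclusion.** The point holds in a limited form. The face-validity objective, as the Study Summary states it, has no planned, systematic measure: 0 of the 2 face-validity questions and 0 of the 10 Appendix 5 Likert statements address it. A claim of face validity would rest on perceived appropriateness, which is a legitimate construct but a different one.

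The consequence is confined to an exploratory, descriptive component with ten respondents. The primary Sim-OSSCAR comparison, the randomisation and the trial sample size are unaffected, and nothing here bears on whether the training improves competence.

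The conclusion assumes that the two listed questions are the whole face-validity instrument and that Appendix 5 is the acceptability survey. The Qualitative analysis section cites an appendix 8, but only six appendices are listed. If another questionnaire exists and contains a representation item, the point falls and that item should be cited in the Face Validity section.

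**What to change.** 1. In the Face Validity section, add at least one item on the existing 5-point scale asking how well the simulator represents real MSICS. Items for each interactive step are optional; each should cover a single attribute. If both appearance and haptic feel are wanted, the set comes to about 19 items.
2. Base the face-validity conclusion on the new item or items, and link the claim in Expected Outcomes of the Study to them.
3. Report the two existing questions under acceptability and utility.
4. If no item is added, reword the Study Summary objective and the Expected Outcomes claim to perceived appropriateness for training and assessment.

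The cost is a few more minutes for each of the ten experts, who already complete a survey, and possibly a less favourable face-validity result. The change should be made before the experts are surveyed; afterwards only the rewording in item 4 remains available.

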## Sample size

Based on pilot and published data we anticipate the mean Sim-OSSCAR score to be 10/40 (standard deviation (SD) 6 points) at baseline. We anticipate an effect size of 2.5 SD in the mean Sim-OSSCAR between groups. We assume a correlation between these observations of 0.8. Variation between clusters (training institutions) will be accounted for with a co-efficient of variation of 0.5.

Therefore, a sample of 52 individuals in total (26 in each arm) would have 80% power and 95% confidence to detect a difference of 15 points (2.5SD). We will recruit 60 participants for the Orbis-FVR training study to provide 8 extra participants as we anticipate a moderate loss to follow-up.

We and our collaborators consider this sample size of 60 participants to be feasible within the available time and financial resources. It would take longer (an extra academic year) if we needed to recruit many more, and if the impact of COVID-19 on training continued throughout the recruitment year.

For the construct validity of the FVR assessment capacity, we will recruit a total of 5 experts and 5 novices from participating centers. Sample sizes of content, face and construct validity study are based on data from recent validation studies of ophthalmic simulation surgical competency assessment rubrics. Additionally, as we predict a large differences between the two participating groups, small cohort numbers suffice. For face validity, we will recruit ten experts from multiple centers, likewise, this was determined based on data from similar face validation studies.

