### Randomisation

#### Sequence generation

The randomization sequences will be computer generated and administered centrally by a statistician based at the QUB who is independent of all other aspects of the trial. We will use block randomization (block size 2 or 4), with a separate sequence for each of the ten recruitment sites, to ensure balance. The statistician will generate the code / sequence (as a block of 2 or 4).

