### Randomization Implementation

Trainees within the same training institution, who have met the appropriate inclusion and exclusion (as detailed previously), will be eligible for randomization to the 'intervention' or 'control' arm. Each group of four trainee participants will be agreed by the Head of Training Program or Department.

For example (Blocks will be in groups of 4, 6 or 8 depending on the institution and the number of residents that meet the inclusion criteria):

A block of four potential participants is identified in Chittagong Eye Institute Training Center (CEITC), Bangladesh. Cards with the allocation or a block of four (two intervention and two control) were printed and placed in sealed opaque envelopes. Physically, in Bangladesh, a block of four identical envelopes (e.g. block number 11) will be selected. Participants will be invited by the Head of Department to pick one of the four envelopes. In this example, CEITC randomization block 11 allocation might be:

IRO1101	Intervention
IRO1102	Control
IRO1103	Control
IRO1104	Intervention

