## Analysis

Statistical analysis

The primary outcome measure (mean Sim-OSSCAR score at 1 month) will be analyzed using a t-test. Performances will be compared between intervention and control groups: these are a continuous variable in each group. We will compare these mean Sim-OSSCAR^1 scores by t-tests (which is unadjusted) and linear regression (adjusting for training center as a fixed effect). An alpha level of  $p < 0.05$  will be considered statistically significant, and a kappa coefficient of  $\geq 0.75$  for inter-rater agreement is considered

excellent.

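### The stated 80% power for 15 points at 26 per arm is not the power of the planned design and tests, which is above 99.99%

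*Combined protocol and SAP*

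**What the plan says.** The Sample size section gives these inputs in turn:

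- Baseline: "we anticipate the mean Sim-OSSCAR score to be 10/40 (standard deviation (SD) 6 points) at baseline".
- An effect of 2.5 SD between groups, that is 15 points.
- "We assume a correlation between these observations of 0.8".
- "Variation between clusters (training institutions) will be accounted for with a co-efficient of variation of 0.5".

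It concludes that 26 per arm "would have 80% power and 95% confidence to detect a difference of 15 points (2.5SD"), and raises 52 to 60 for loss to follow-up.

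The design and analysis are described elsewhere in the combined document:

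- Sequence generation uses block randomisation "with a separate sequence for each of the ten recruitment sites, to ensure balance".
- Randomization Implementation confirms that the unit is the individual: "Trainees within the same training institution, who have met the appropriate inclusion and exclusion (as detailed previously), will be eligible for randomization" to either arm.
- Statistical analysis says: "The primary outcome measure (mean Sim-OSSCAR score at 1 month) will be analyzed using a t-test". The comparison is made "by t-tests (which is unadjusted) and linear regression (adjusting for training center as a fixed effect").

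Study Setting and Study Participants both count 9 institutions, against ten under Sequence generation.

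**The concern.** An effect of 2.5 SD is very large. When individuals are randomised within site, a handful per arm is enough to detect it, so 80% power at 26 per arm looks far too low. The reference to clusters suggests a calculation for a design in which sites, not trainees, are the unit of comparison.

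What is at stake is interpretation. A reader who takes the paragraph at face value will think that the trial is just large enough to see 15 points, when the planned tests could detect a difference about a third of that size. A null or modest result would then be judged against the wrong benchmark. The Executive Summary calls the study a pilot whose results will inform a later multi-centre trial, so the calculation could also be copied forward.

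**Working it through.** **Inputs.** From Sample size: 26 per arm, difference δ = 15, SD σ = 6 (given for baseline only), baseline mean 10, coefficient of variation k = 0.5. The intervention mean is taken as 10 + 15 = 25. Assumptions: 95% confidence means a two-sided 5% level, σ = 6 also holds at one month, and the arms are balanced within each site.

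**1. A route to the plan's 80%.** The planned tests do not give it (step 2). A matched cluster-level formula comes close. With c sites and m = 26/c trainees per site per arm:

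V = 2σ²/m + k²(10² + 25²) = 72/m + 181.25

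power = Φ(√[(c − 2)·δ²/V] − 1.96)

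- c = 9: m = 2.89, V = 24.92 + 181.25 = 206.2. √(7 × 225/206.2) = 2.764. Power = Φ(0.804) = 78.9%.
- c = 10: m = 2.6, V = 27.69 + 181.25 = 208.9. √(8 × 225/208.9) = 2.935. Power = Φ(0.975) = 83.5%.

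The unmatched version of the formula gives 26.3 per arm if 3.25 trainees per site per arm are assumed, but 17 per arm at 2 and 39 per arm at 5. These routes let the mean of each arm at each site vary independently, make no use of the 0.8 correlation, and need a number of sites or a cluster size that the section does not state.

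**2. Power of the planned t-test.** Noncentral t with 2n − 2 degrees of freedom and noncentrality δ/(σ√(2/n)):

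| n per arm | Noncentrality | Power for 15 points |
|---|---|---|
| 3 | 3.06 | 63.6% |
| 4 | 3.54 | 83.6% |
| 26 | 9.01 | above 99.99% |

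For 26 per arm to give only 80%, the SD would have to be 18.9 points on a 40-point scale.

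**3. Difference detectable with 80% power at 26 per arm.**

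- Normal approximation: (1.960 + 0.842) × 6 × √(2/26) = 4.66 points.
- t-test, 50 degrees of freedom, 6 taken as the total SD: 4.75 points (0.79 SD).
- Regression with centre fixed effects, 6 taken as the within-site SD: 4.77 points with 9 sites (52 − 9 − 1 = 42 degrees of freedom) and 4.77 to 4.78 with 10 (41 degrees of freedom).

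**4. Site variation under within-site blocking.** Site effects shared by both arms largely cancel from the difference between arms. They drop out of the centre-adjusted regression. In the unadjusted t-test they only inflate the standard error. Simulation with equal arms within each of 9 or 10 sites and a within-site SD of 6 puts 80% t-test power at about 5.7 points for a site SD of 5 (0.5 × 10). Even with a site SD of 12.5 (0.5 × 25), power for 15 points is about 99.9% or more. Adding the site variance as plain independent noise, as if randomisation were not blocked by site, would overstate the detectable difference.

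**5. Loss to follow-up.** 52/(1 − 8/60) = 60. This part is consistent.

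**The case against.** The best defence is that the authors used a cautious cluster calculation on purpose. Step 1 shows that their inputs can lead to about 26 per arm that way, so it would be unfair to say that the figure cannot be obtained or that the arithmetic slipped. That stands: this is a mismatch between calculation and design. It is also conservative, the section supports 60 on feasibility as well, and the Executive Summary describes a pilot. All of this keeps the severity low.

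Three stronger readings are tempting, and the documents do not support them.

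- **The trial is underpowered, or should be cut.** It is not underpowered for 15 points. Nor does the 4-per-arm figure argue for fewer participants: it depends on an effect of 2.5 SD and on a baseline SD carried over to one month.
- **Site variation seriously erodes power.** If site effects are common to both arms, step 4 shows that it does not.
- **The planned tests have an inflated false-positive rate.** This needs the training effect itself to vary between sites, whereas the section speaks only of variation between institutions. Even on that reading the size is open. With no average effect both means are 10, so k = 0.5 gives a site SD of 5 in each arm. Simulated rejection is then about 14% to 15% (t-test) and 17% to 18% (regression) if the arms' site effects are independent, but 3% to 4% and about 8% if they correlate at 0.8. If training has no effect at any site, the regression rejects in 5% and the t-test in fewer.

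**Conclusion.** The point holds as a mismatch between the power statement and the design, with low severity. For the randomisation and tests that the plan describes, power for 15 points at 26 per arm is above 99.99%, not 80%, and 80% power falls at about 4.8 points (0.79 SD). This rests on a one-month SD of 6, a two-sided 5% level and site effects common to both arms. If the unadjusted t-test must also carry a common site SD of 5, the 80% point moves to about 5.7 points.

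The section leaves unstated the formula, the number of sites or cluster size, the one-month SD and which observations the 0.8 correlation links. It could link baseline with one month, the three cases, or the arms' site means. If it is baseline with one month, using it would need a baseline adjustment that Statistical analysis does not include.

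**What to change.** Keep 52 evaluable and 60 recruited, and rewrite the power statement for the planned analysis. For example:

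> *Assuming a one-month within-site SD of 6 and site effects common to both arms, 26 per arm gives over 99% power (two-sided 5%) for 15 points, and the centre-adjusted regression has 80% power for about 4.8 points (0.8 SD).*

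In addition:

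- If a t-test figure that includes site variation is wanted, compute it under within-site blocking (about 5.7 points at a site SD of 5).
- Remove the cluster coefficient of variation from the calculation. If variation of the training effect between sites is intended, state the formula and the number of sites, and bring Statistical analysis into line with it.
- Say which observations the 0.8 correlation links.
- Reconcile the site count: 9 in Study Setting and Study Participants, ten in Sequence generation.

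The cost is one reworded paragraph and a corrected site count, plus a sentence in Statistical analysis only if variation in effect is intended. No participants or procedures are added.
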